## 8. STATISTICAL CONSIDERATIONS

### 8.1. Analysis Objectives and Endpoints

#### 8.1.1. Analysis Objectives

The primary objectives of this study are as follows:

- To evaluate the efficacy of RDV in reducing the rate of COVID-19 related hospitalization or all-cause death when given over 3 days to non-hospitalized participants with early stage COVID-19
- To evaluate the safety of RDV administered in an outpatient setting

The secondary objectives of this study are as follows:

- To evaluate the efficacy of RDV in reducing the rate of COVID-19 related MAVs (medical visits attended in person by the participant and a health care professional) or all-cause death in non-hospitalized participants with early stage COVID-19. An MAV includes in-person clinic visit, urgent care visit, emergency room visit, or hospitalization
- To determine the antiviral activity of RDV on SARS-CoV-2 viral load
- To assess the impact of RDV on symptom duration and severity

CCI

A large rectangular area of the page is completely blacked out, representing redacted content. The word 'CCI' is printed in red at the top left corner of this redacted area.

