### **8.9. Sample Size**

The total sample size of the study will be approximately 1264 participants.

The sample size computation is based on proportions of COVID-19 related hospitalization or all-cause death by Day 28 for the RDV and placebo treatment groups. The sample size needed for a 1:1 randomization using a 2-tailed test at level  $\alpha$  is given by:

$$\frac{(z_{1-\alpha/2} + z_{1-\beta})^2}{P(1 - R^2)\sigma^2 B^2}$$

Where P is the overall rate of COVID-19 related hospitalization or all-cause death, B is the log hazard ratio,  $\sigma$  is the standard deviation of treatment indicator variable, R is the R-Squared that is obtained when treatment indicator variable is regressed on the other covariates, and  $z_{1-\alpha/2}$  and  $z_{1-\beta}$  are the 1- $\alpha/2$  and 1- $\beta$  quantiles of the standard normal distribution.

A sample size of 1264 participants (632 in each group with 1:1 randomization) achieves > 90% power to detect a ratio of 0.55 (RDV to placebo in proportion of COVID-19 related hospitalization or all-cause death, which is equal to a hazard ratio of 0.534) using a 2-sided significance level of 0.05 assuming the overall hospitalization or death rate is 9.3% (12% in the placebo group and 6.6% in the RDV group) and a 5% drop out rate. The sample size provides approximately 80% power to detect smaller treatment effect size with a ratio of 0.60 (RDV to placebo), assuming a 2-sided significance level of 0.05 and the overall hospitalization or death rate is 9.6% (12% in the placebo group and 7.2% in the RDV group) and a 5% drop out rate.

The sample size calculation was done using software PASS (Version 14.0, module of Cox regression for survival).

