### 1.3. Sample Size and Power

The total sample size of the study will be approximately 1264 participants.

The sample size computation is based on proportions of COVID-19 related hospitalization or all-cause death by Day 28 for the RDV and placebo treatment groups. The sample size needed for a 1:1 randomization using a 2-tailed test at level  $\alpha$  is given by:

$$\frac{(z_{1-\alpha/2} + z_{1-\beta})^2}{P(1 - R^2)\sigma^2 B^2}$$

Where  $P$  is the overall rate of COVID-19 related hospitalization or all-cause death,  $B$  is the log hazard ratio,  $\sigma$  is the standard deviation of treatment indicator variable,  $R$  is the R-Squared that is obtained when treatment indicator variable is regressed on the other covariates, and  $z_{1-\alpha/2}$  and  $z_{1-\beta}$  are the 1- $\alpha/2$  and 1- $\beta$  quantiles of the standard normal distribution.

A sample size of 1264 participants (632 in each group with 1:1 randomization) achieves  $> 90\%$  power to detect a ratio of 0.55 (RDV to placebo) in proportion of COVID-19 related hospitalization or all-cause death, which is equal to a hazard ratio of 0.534) using a two-sided significance level of 0.05 assuming the overall COVID-19 related hospitalization or all-cause death rate is 9.3% (12% in the placebo group and 6.6% in the RDV group) and a 5% drop out rate. The sample size provides approximately 80% power to detect a smaller treatment effect size with a ratio of 0.60 (RDV to placebo), assuming a 2-sided significance level of 0.05 and the overall COVID-19 related hospitalization or all-cause death rate is 9.6% (12% in the placebo group and 7.2% in the RDV group) and a 5% drop out rate. The proportion of patients with COVID-19-related hospitalizations or emergency department (ED) visits was 13.5% in high risk patients (age  $\geq 65$  or BMI  $\geq 35$ ) who received placebo {[Gottlieb 2021](#)}, 12% is assumed for the study to account for decrease in hospitalization rate in recent months.

The sample size calculation was done using software PASS (Version 14.0, module of Cox regression for survival).

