### **2.3. Changes from Protocol-Specified Analyses**

The DMC analysis was not performed due to the stop of enrollment on 08 April 2021 after less than 50% of the participants were randomized. The reasons of stopping enrollment were due to significant changes in the epidemiology of COVID-19 from a combination of lower hospitalization rates and high vaccine rates in high-risk patients, and a change in the unmet patient need for convenient at home options for non-hospitalized patients with COIVD-19. The decision to stop study enrollment was documented on 06-APR-2021 Study Management Team meeting minutes.

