## 6. EFFICACY ANALYSES

### 6.1. Primary Efficacy Endpoint

#### 6.1.1. Definition of the Primary Efficacy Endpoint

The primary endpoint of the study is the composite endpoint of COVID-19 related hospitalization (defined as at least 24 hours of acute care) or all-cause death by Day 28. The endpoint will be derived by combining the available all-cause death and COVID-19 related hospitalization reported by the site. The first COVID-19 related hospitalization will be used for the proportion of COVID-19 related hospitalization or all-cause death.

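### The SAP's 12% placebo rate is not justified for this endpoint, and its power statement still describes 1264 participants although enrolment stopped at 584

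*SAP*

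**What the plan says.** **Stated power.** SAP 1.3 says "A sample size of 1264 participants (632 in each group with 1:1 randomization") has more than 90% power for a risk ratio of 0.55 (hazard ratio 0.534) and about 80% for 0.60, "using a two-sided significance level of 0.05". The assumptions are a 12% placebo rate and 5% dropout. Protocol 8.9 gives the same figures ("achieves > 90% power to detect a ratio of 0.55").

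**Source of the 12%.** SAP 1.3: "The proportion of patients with COVID-19-related hospitalizations or emergency department (ED) visits was 13.5% in high risk patients", defined there as age at least 65 or BMI at least 35, on placebo in one outside trial. The reduction is explained in one clause: "12% is assumed for the study to account for decrease in hospitalization rate in recent months".

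**Endpoint being powered.** SAP 6.1.1: "COVID-19 related hospitalization (defined as at least 24 hours of acute care) or all-cause death by Day 28". ED visits belong to the secondary endpoint of medically attended visits. Protocol 8.1.1: "An MAV includes in-person clinic visit, urgent care visit, emergency room visit, or hospitalization".

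**Safeguard and outcome.** Protocol 8.9.1 plans a sample size re-estimation at about half of participants through Day 28, because the placebo rate was uncertain, with a cap of 1500. SAP 2.1.1 records that this interim look did not take place and that enrolment stopped after 584 were randomized. SAP 2.3 gives the reasons for stopping, which include "lower hospitalization rates and high vaccine rates in high-risk patients".

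**The concern.** The benchmark counts a broader event than the one being powered. An ED visit shorter than 24 hours adds to the 13.5% but cannot add to this trial's primary endpoint. The only adjustment described is for calendar time. None is described for removing ED-only visits, or for entry criteria that differ from the benchmark's (here age 60 or over, BMI 30 or over, or any one of several other conditions).

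SAP 1.3 also presents the 1264-participant power without qualification, although SAP 2.1.1 reports that fewer than half that number were randomized. At stake is how a non-significant result is read. Someone who takes the stated power at face value would treat such a result as fairly strong evidence against a benefit of the planned size. The trial as run cannot supply that evidence.

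**Working it through.** **Inputs.** From SAP 1.3: two-sided alpha 0.05, N = 1264 allocated 1:1, dropout 5%, placebo rate p_c = 12%, ratios 0.55 and 0.60. From SAP 2.1.1: 584 randomized. From Protocol 8.9.1: cap of 1500. One assumption of mine: R² = 0 in the SAP's formula, since no value is given.

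**Formulas.** p_t = ratio × p_c. HR = ln(1 − p_t) / ln(1 − p_c). Events = N × 0.95 × (p_c + p_t)/2. Power = Φ(√(events/4) × |ln HR| − 1.96). This is the SAP's Cox formula with σ² = 0.25, solved for power.

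**Step 1: reproduce the stated figures.**
- Ratio 0.55: p_t = 6.6%, HR = 0.534, events = 1264 × 0.95 × 0.093 = 111.7, power = Φ(3.314 − 1.960) = 91.2%. Stated: above 90%.
- Ratio 0.60: p_t = 7.2%, HR = 0.5845, events = 1264 × 0.95 × 0.096 = 115.3, power = Φ(2.882 − 1.960) = 82.2%. Stated: about 80%.

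The calculation is sound given 12%. The question is the input.

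**Step 2: how much room is there?** At 1264, power for ratio 0.55 reaches 90% at p_c = 11.5%, and power for ratio 0.60 reaches 80% at p_c = 11.4%. A shortfall of 0.5 to 0.6 percentage points therefore removes both stated levels. As a share of the 12%, that is about 4% to 5%.

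**Step 3: effect of removing ED-only visits.** The documents do not give the ED-only share, so the shares below are assumed. The SAP's calendar adjustment is kept: p_c = 13.5% × (12/13.5) × (1 − share) = 12% × (1 − share). N = 1264, 5% dropout.

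| Assumed ED-only share | Placebo rate | Power, ratio 0.55 | Power, ratio 0.60 |
|---|---|---|---|
| none (SAP) | 12% | 91% | 82% |
| 10% | 10.8% | 88% | 78% |
| 20% | 9.6% | 84% | 72% |
| one third | 8% | 76% | 64% |
| one half | 6% | 63% | 51% |

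**Step 4: what the re-estimation could have recovered.** At the cap of 1500 with 5% dropout, power for ratios 0.55 and 0.60 is 90.5% and 81% at a 10% placebo rate, 83% and 71% at 8%, and 70% and 58% at 6%.

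**Step 5: the trial as enrolled.** N = 584, 5% dropout.

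| Placebo rate | Expected events, ratio 0.55 | Power, ratio 0.55 | Power, ratio 0.60 |
|---|---|---|---|
| 12% | 52 | 61% | 50% |
| 8% | 34 | 44% | 35% |
| 5% | 22 | 29% | 23% |

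At the SAP's own 12%, stopping early takes ratio 0.55 from 91.2% to 61.5%, about 30 points, before any doubt about the benchmark.

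**The case against.** The strongest reply is that nothing here shows 12% to be wrong. The stated power is correct at 12%, and whether 12% is too high depends on an ED-only share that neither document gives. The primary endpoint also adds all-cause death, which pushes the rate up. All of this stands. A reader might infer that the power is overstated as a matter of fact, or that the one-third and one-half rows show the expected loss. The documents support neither: those shares are illustrations, and 10% or 20% is equally compatible with the text. What remains is that deaths would have to offset almost all ED-only visits to keep 12%, and the SAP does not argue that they do.

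A reader might also infer that the benchmark came from a higher-risk group. Its age and BMI cut-offs are stricter, but this trial also admits immunocompromised participants, those with current cancer and nursing-facility residents. The net difference in risk could go either way.

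Nor does the reason for stopping show that the design rate was wrong. SAP 2.3 describes later epidemiological change, which concerns the calendar trend and not the endpoint definition.

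The sponsor did recognise the uncertainty and planned a re-estimation for it, which could have covered a modest shortfall (Step 4). It was not performed, so it offers no protection now.

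Finally, SAP 6.1.3 already reports the hazard ratio with its 95% confidence interval, and no passage says that a null result will be judged against the power statement. That limits the consequence, but it does not make a 1264-participant power figure describe 584 participants.

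**Conclusion.** The concern holds in a limited form. The 12% placebo rate is not justified for an endpoint of at least 24 hours of acute care or death, because its source counts ED visits and the only stated adjustment is for calendar time. The stated power is probably optimistic. The direction is a reasonable inference, and the amount cannot be fixed from the documents. The stated levels leave little room, since about half a percentage point on the placebo rate removes both.

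The firmer part needs no assumption about the benchmark. At 584 randomized and the SAP's own 12%, power is about 61% for ratio 0.55 and 50% for ratio 0.60, against the stated levels of above 90% and about 80%. These figures assume R² = 0 and the planned 5% dropout. The early stop costs more power than any benchmark error of modest size. This is a weakness in an input and in an outdated statement, not an arithmetic error.

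**What to change.** In SAP 1.3:

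1. Label the above-90% and about-80% figures as the original design at 1264 participants.
2. State that the benchmark includes ED visits and used different age and BMI criteria, without describing it as higher-risk, and that 12% is an assumption.
3. Add power at the 584 randomized over placebo rates of 5% to 12%. For ratio 0.55 this is 29% at 5%, 44% at 8% and 61% at 12%; for ratio 0.60 it is 23%, 35% and 50%.
4. State that a non-significant primary result will be read from the 95% confidence interval of the hazard ratio.

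The cost is a few sentences and a small table, and a stated power that looks less favourable. Enrolment, endpoints and analyses do not change.

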## **2. TYPE OF PLANNED ANALYSIS**

### **2.1. Interim Analyses**

Prior to the final analysis, interim analyses may be conducted, and the analyses may be submitted to regulatory agencies to seek guidance for the overall clinical development program.

#### **2.1.1. DMC Analysis**

One external multidisciplinary DMC was planned to review the progress of the study and to perform interim reviews of the efficacy (futility assessment) and safety data. However, this DMC analysis was not performed due to the stop of study enrollment after 584 participants randomized and prior to reaching the planned DMC analysis schedule (ie, approximately 50% of the total 1264 planned participants have completed Day 28 assessment).

### **2.2. Final Analysis**

The final analysis will be performed after all participants have completed or discontinued from the study, outstanding data queries have been resolved or adjudicated as unresolvable, and the data have been cleaned and finalized. This SAP describes the analysis plan for the final analysis.

### **2.3. Changes from Protocol-Specified Analyses**

The DMC analysis was not performed due to the stop of enrollment on 08 April 2021 after less than 50% of the participants were randomized. The reasons of stopping enrollment were due to significant changes in the epidemiology of COVID-19 from a combination of lower hospitalization rates and high vaccine rates in high-risk patients, and a change in the unmet patient need for convenient at home options for non-hospitalized patients with COIVD-19. The decision to stop study enrollment was documented on 06-APR-2021 Study Management Team meeting minutes.

### **3. GENERAL CONSIDERATIONS FOR DATA ANALYSES**

Analysis results will be presented using descriptive statistics. For categorical variables, the number and percentage of participants in each category will be presented; for continuous variables, the number of participants (n), mean, standard deviation (SD) or standard error (SE), median, first quartile (Q1), third quartile (Q3), minimum, and maximum will be presented.

All statistical tests will be 2-sided and performed at the 5% significance level unless otherwise specified.

By-subject listings will be presented for all participants in the All Randomized Analysis Set and sorted by subject ID number, visit date, and time (if applicable). Data collected on log forms, such as AEs, will be presented in chronological order within the participant. The treatment group to which participants were randomized will be used in the listings. Age, sex at birth, race, and ethnicity will be included in the listings, as space permits.

#### **3.1. Analysis Sets**

Analysis sets define the participants to be included in an analysis. Analysis sets and their definitions are provided in this section. Participants included in each analysis set will be determined before the study blind is broken for analysis. The analysis set will be identified and included as a subtitle of each table, figure, and listing.

For each analysis set, the number and percentage of participants eligible for inclusion, will be summarized by treatment group.

A listing of reasons for exclusion from analysis sets will be provided by participant.

##### **3.1.1. All Randomized Analysis Set**

All Randomized Analysis Set includes all participants who were randomized in the study.

##### **3.1.2. Full Analysis Set**

The primary analysis set for efficacy analysis is defined as the Full Analysis Set (FAS), which will include all participants who (1) are randomized into the study, and (2) have received at least 1 dose of study treatment. Participants will be grouped according to the treatment to which they were randomized.

##### **3.1.3. Modified Full Analysis Set**

A modified full analysis set (mFAS) includes all participants who (1) are randomized into the study, and (2) have received at least 1 dose of study treatment, and (3) enrolled under protocol amendment 2 or later. Participants will be grouped according to the treatment to which they were randomized.

### **3.1.4. Safety Analysis Set**

The primary analysis set for safety analyses is defined as the Safety Analysis Set, which will include all participants who (1) are randomized into the study and (2) have received at least 1 dose of study treatment. Participants will be grouped according to the treatment which they received.

CCI [REDACTED]

[REDACTED]

[REDACTED]

CCI [REDACTED]

[REDACTED]

[REDACTED]

### **3.1.7. Virology Analysis Set**

The Virology Analysis Set will include all participants who (1) are randomized into the study, (2) have received at least 1 dose of study treatment, and (3) have positive SARS-CoV-2 viral load at baseline (result of ‘No SARS-CoV-2 detected’ is considered as negative, results of ‘Inconclusive’, “<2228cp/mL SARSCoV2 detected” and numerical results are considered as positive).

## **3.2. Subject Grouping**

For analyses based on the All Randomized Analysis Set, FAS, mFAS or Virology Analysis Set, participants will be grouped according to the treatment to which they were randomized. For the safety analysis set, the actual treatment received will differ from the randomized treatment only when their actual treatment differs from randomized treatment for the entire treatment duration.

CCI [REDACTED]

[REDACTED]

## **3.3. Strata and Covariates**

Participants will be randomly assigned to treatment groups via the interactive voice or web response system (IXRS) in a 1:1 ratio using a stratified randomization schedule. Stratification will be based on the following variables:

- Region: US vs. ex-US
- Participant’s age: < 60 vs  $\geq$  60 years
- Resident of skilled nursing facility: Yes vs. No

Stratification discrepancies will be reviewed and assessed. The values recorded in the clinical database will be used for analyses in case there are discrepancies between the IXRS and the clinical database. Based on the assessment of stratification discrepancies, a sensitivity analysis of the primary endpoint may be performed.

The primary efficacy endpoint will be evaluated in a stratified analysis based on the same 3 factors used for randomization, as specified in Section 6.1.3. In addition, observed imbalances between treatment groups in other baseline characteristics may be considered as covariates in sensitivity analyses of efficacy endpoints.

### **3.4. Examination of Subject Subgroups**

The primary endpoint will be examined for the following participant subgroups:

- region (US vs. ex-US)
- participant's age (<18, 18≤ - < 60, ≥ 60 years),
- participants who reside in a skilled nursing facility (Yes, No),
- Sex at birth: (a) male and (b) female
- Race: (a) Asian, (b) Black, (c)White, (d) other
- Baseline risk factor: Chronic lung disease (Yes, No), Hypertension (Yes, No), Cardiovascular or cerebrovascular disease (Yes, No), Diabetes mellitus (Yes, No), Obesity (Yes, No), Immunocompromised state (Yes, No), Chronic mild or moderate kidney disease (Yes, No), Chronic liver disease (Yes, No), Current cancer (Yes, No), Sickle cell disease (Yes, No)
- Common COVID-19 symptoms at baseline: absence or presence for each of the following symptoms: Stuffy or runny nose; Sore throat; Shortness of breath (difficulty breathing); Cough; Low energy or tiredness; Muscle or body aches; Headache; Chills or shivering; Feeling hot or feverish; Nausea; Vomit; Diarrhea; Loss of Smell; Loss of taste.

In addition, other subgroups may be considered based on imbalances between treatment groups observed in other baseline characteristics.

### **3.5. Multiple Comparisons**

There will be no multiplicity adjustment in the final analysis. Efficacy will be evaluated using the primary efficacy endpoint at the significance level of 0.05. All other efficacy endpoints are exploratory in nature and will be tested using 2-sided tests at the 5% significance level without multiplicity adjustment.

### **3.6. Missing Data and Outliers**

#### **3.6.1. Missing Data**

In general, missing data will not be imputed unless methods for handling missing data are specified. Exceptions are presented in this document.

Participants with missing outcomes for the primary endpoint due to premature discontinuation of the study will be censored at last study date.

In this study, a missing pre-treatment laboratory result would be treated as normal (ie, no toxicity grade) for the laboratory abnormality summary. The handling of missing or incomplete dates for AE onset is described in Section 7.1.6.2, and for prior and concomitant medications in Section 7.4.

#### **3.6.2. Outliers**

Outliers will be identified during the data management and data analysis process. No sensitivity analyses to evaluate the impact of outliers on efficacy or safety outcomes are planned. Unless specified otherwise, all data will be included in the analyses.

### **3.7. Data Handling Conventions and Transformations**

In general, age collected at Day 1 (in years) will be used for analyses and presented in listings. If age at Day 1 is not available for a participant, then age derived based on date of birth and the first dose date will be used instead. If an enrolled participant was not dosed with any study drug, the randomization date will be used instead of the Day 1 visit date. For screen failures, the date the first informed consent was signed will be used for the age derivation. Age required for longitudinal and temporal calculations and analyses (e.g., estimates of creatinine clearance, age at date of AE) will be based on age derived from date of birth and the date of the measurement or event, unless otherwise specified.

The following conventions will be used for the imputation of date of birth when it is partially missing or not collected:

- If only year of birth is collected, then “01 July” will be imputed as the day and month of birth
- If year of birth is missing, then date of birth will not be imputed.

Laboratory data that are continuous in nature but are less than the lower limit of quantitation (LOQ) or above the upper LOQ will be imputed as follows:

- A value that is 1 unit less than the LOQ will be used to calculate descriptive statistics if the datum is reported in the form of “ $< x$ ” (where x is considered the LOQ). For example, if the values are reported as  $< 50$  and  $< 5.0$ , values of 49 and 4.9, respectively, will be used to calculate summary statistics. An exception to this rule is any value reported as  $< 1$  or  $< 0.1$ , etc. For values reported as  $< 1$  or  $< 0.1$ , a value of 0.9 or 0.09, respectively, will be used to calculate summary statistics.
- A value that is 1 unit above the LOQ will be used to calculate descriptive statistics if the datum is reported in the form of “ $> x$ ” (where x is considered the LOQ). Values with decimal points will follow the same logic as above.
- The LOQ will be used to calculate descriptive statistics if the datum is reported in the form of “ $\leq x$ ” or “ $\geq x$ ” (where x is considered the LOQ).

SARS-CoV2 viral load results that are below LOQ but have a positive signal will be reported as “ $<2228\text{cp/mL SARSCoV2 detected}$ ” and those that are below lower limit of detection(LOD) and negative will be reported as “No SARS-CoV2 detected”. The data will be imputed as follows:

- A value of 1114 copies/ml (half of the LOQ 2228 copies/ml) will be used to calculated descriptive statistics if the datum is reported as “ $<2228\text{cp/mL SARSCoV2 detected}$ ”.
- A value of 746.5 copies/ml (1/2 of the LOD 1493 copies/ml) will be used to calculated descriptive statistics if the datum is reported as “No SARS-CoV2 detected”

Any SARS-CoV-2 viral load samples collected on or after the participants are receiving additional COVID-19 treatments (see [Appendix 2](#)) will be excluded from the viral load analysis.

Base 10 logarithm transformation will be used for analyzing SARS-CoV-2 viral load.

CCI

